5.9 SAFETY ANALYSES

All safety parameters will be analyzed descriptively for the Safety Population.

TEAEs will be summarized by treatment arm with PT under SOC. Listings will be provided for screening (pretreatment), run-in, and treatment period TEAEs; severe TEAEs, study drug-related TEAEs, SAEs, and TEAEs leading to study discontinuation. Descriptive statistics will be provided for all safety parameters (ECGs, vital signs, and clinical laboratory tests).

ECGs, vital signs, and clinical laboratory tests will be summarized at each timepoint and listings will be provided for patients with abnormal values.

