5.9.3 ECGs

Descriptive statistics for ECG parameters and changes from the baseline values at the end of treatment visit will be presented by treatment arm for the Safety Population.

The number and percentage of patients with ECG abnormalities will be tabulated by treatment arm. Shift tables will be presented comparing values between baseline and end of study. A listing of all AEs for patients with ECG abnormalities will also be provided.

The number and percentage of patients with absolute QTcF intervals in the following categories will be examined: $QTcF \leq 450$ ms, $450 \text{ ms} < QTcF \leq 480$ ms, $480 \text{ ms} < QTcF \leq 500$ ms, and $QTcF > 500$ ms. Shift tables will be presented comparing values between baseline and end of study.

Additionally, the number and percentage of patients with a change from baseline in QTcF interval according to the following categories will be examined: QTcF interval increases by more than 30 ms, but not more than 60 ms, and QTcF interval increases by more than 60 ms. Shift tables will be presented comparing values between baseline and end of study.

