## 7.5. ECG 12-Lead Electrocardiogram (ECG)

12-lead ECG measurements will be performed at the scheduled time points, including the heart rate (HR), QT interval, RR interval, PR interval, or QTcF – Fridericia's Correction Formula. ECG overall result will also be collected on the electronic case report form (eCRF). If QTc result is outside of normal range, perform in triplicate and calculate the average. If ECG result is clinically abnormal, repeat.

This document is confidential.

Descriptive statistics for ECG parameters and changes from the baseline (Day 1) values at Week 1 and the end of treatment (EOT) visit will be presented by treatment group for the Safety Population. Change from predose to postdose for ECG parameters will also be calculated for the Day 1, Week 1, and EOT visits and summarized by treatment group. For ECG triplicates, the mean will be presented as the participant's value at a given visit.

The number and percentage of participants with absolute QTcF intervals in the following categories will be tabulated by treatment group: QTcF  $\leq$  450 ms, 450 ms  $<$  QTcF  $\leq$  480 ms, 480 ms  $<$  QTcF  $\leq$  500 ms, and QTcF  $>$  500 ms. Shift tables will be presented comparing values between baseline and Week 1 and EOT.

The number and percentage of participants with absolute HR in the following categories will be tabulated by treatment group:  $\leq$  50 bpm, 50 bpm  $<$  HR  $<$  110 bpm, and HR  $\geq$  110 bpm. Shift tables will be presented comparing values between baseline and Week 1 and EOT.

The number and percentage of participants with a change from baseline in QTcF interval according to the following categories will be examined: QTcF interval increases by more than 30 ms but not more than 60 ms, and QTcF interval increases by more than 60 ms.

Additionally, the number and percentages of participants with a change from baseline in HR according to the following categories will be examined: HR increases by more than 10 bpm but not more than 30 bpm, and HR increases by more than 30 bpm. Additionally, the number and percent of participants with a change from baseline in HR corresponding to a 20% increase or more will be calculated.

All ECG data will be listed. In addition, a listing of all AEs for participants with a QTcF increase of more than 30 ms or an HR increase of more than 30 bpm will be provided.

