## 11. Changes from Analysis Planned in Protocol

In Protocol Section 4.2.3 (patient-reported outcomes), both number and proportion of days of work/school missed due to SCD symptoms at Weeks 4, 8, 12 were included.

However, current SAP will summarize and analyze only the number (not proportion) of days of work/school missed due to SCD symptoms at Weeks 4, 8, 12. Since each week has 7 days, the calculated proportion of days of interest doesn't provide additional information.

This document is confidential.

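### SAP 7.5 omits, in the text available, the by-arm table of ECG abnormalities planned in Protocol 5.9.3 and narrows the linked AE listing to QTcF and heart-rate rises; Section 11 declares neither change

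*SAP*

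**What the plan says.** **Protocol 5.9.3 (ECGs).** The section opens its categorical outputs with two general ones. The first reads "The number and percentage of patients with ECG abnormalities will be tabulated by treatment arm", followed by shift tables from baseline to end of study. The second reads "A listing of all AEs for patients with ECG abnormalities will also be provided". The QTcF bands and QTcF change categories come afterwards as further outputs. Protocol 5.9 adds, for ECGs, vital signs and laboratory tests, that "listings will be provided for patients with abnormal values".

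**SAP 7.5.** It states that the "ECG overall result will also be collected on the electronic case report form (eCRF"), and the rest of the section does not use that field in a table. The patient counts are these:
- "The number and percentage of participants with absolute QTcF intervals in the following categories will be tabulated by treatment group", with QTcF change categories;
- "The number and percentage of participants with absolute HR in the following categories will be tabulated by treatment group", with heart-rate change categories.

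The AE output is a "listing of all AEs for participants with a QTcF increase of more than 30 ms or an HR increase" of more than 30 bpm. The section also gives descriptive statistics for the ECG parameters (heart rate, QT, RR, PR, QTcF) and lists all ECG data.

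**SAP 2 and 11.** Section 2 lets the SAP override the protocol's statistical text, but requires changes to be documented in Section 11 and substantial differences to be identified. Section 11 contains one entry, on absences: the "current SAP will summarize and analyze only the number (not proportion) of days of work/school missed".

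**The concern.** SAP 7 names the ECG among the data on which safety is assessed. For that data source the protocol planned a simple by-arm count of abnormal patients and a way to read those patients' adverse events together. The SAP text replaces this with interval and rate thresholds. A patient with a new rhythm disturbance, an ischemic pattern or a conduction abnormality not reflected in PR can have an unremarkable QTcF and heart rate. That patient then falls in the normal bands of every ECG count and does not trigger the AE listing.

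At stake is the by-arm view of such findings when they do not become TEAEs. Someone comparing the study report with the protocol would also find a planned safety table missing without explanation.

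**Working it through.** No figure in the plan needs reproducing, so the check is mainly a comparison of text.

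**1. Planned output against SAP output**

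| Output | Protocol 5.9.3 | SAP 7.5 |
|---|---|---|
| Count of patients with ECG abnormalities, by arm | Yes | Not in the text |
| Listing of AEs | Patients with ECG abnormalities | QTcF rise >30 ms or HR rise >30 bpm only |
| QTcF bands and change categories | Yes | Yes |
| HR bands and change categories | No | Added |
| End point of the shift tables | End of study | Week 1 and EOT |

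The protocol gives the QTcF categories as further items after the abnormality table. They therefore cannot serve as its definition of an ECG abnormality, and keeping them does not deliver the table.

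**2. Is the change declared?** No. Section 11 has only the work/school entry.

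**3. Does AE reporting make up for the table?** In part.
- Protocol 3.8.8.7 makes an ECG change an AE if the Investigator considers it clinically significant and it is not already tied to an AE. With onset in the TEAE window, it enters the SAP 7.2 tables by SOC and PT, severity and relationship.
- A finding not judged clinically significant does not take this route.
- Timing excludes a second group. SAP 5.2.4 closes the TEAE window 7 days after the last dose. The Follow-up Visit is 28 (-3/+7) days after the last dose, so from 28 − 3 = 25 to 28 + 7 = 35 days. The earliest visit in that window is 25 − 7 = 18 days after the TEAE window closes. A nonserious abnormality first seen at the Follow-up ECG and dated to it is outside every TEAE table, even if clinically significant. A serious one within 28 days of the last dose reaches the on-therapy SAE table.

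**4. Do the other ECG summaries capture the Follow-up ECG?** As the Schedules of Events read in the text, the post-baseline ECGs are at Day 1 (4 h postdose), Week 1 and Follow-up. SAP 5.4 ends the on-treatment period for non-TEAE endpoints 4 days after the last dose. An ECG at 25 to 35 days is therefore neither Week 1 nor EOT, the two time points of the SAP 7.5 shift tables.

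**5. Weight of one patient.** About 48 patients are randomized 3:1 from Amendment 4 on: 48 × 3/4 = 36 on 18 mg and 48 × 1/4 = 12 on placebo. One patient is 1/36 = 2.8% or 1/12 = 8.3%. This shows how coarse the percentages are. It does not estimate how many cases would be missed.

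**The case against.** A reader might infer that rhythm, conduction and ischemic abnormalities reach no summary of the primary safety objective. The documents do not support that. The primary endpoint is TEAEs (Protocol 4.1.1), and an ECG change judged clinically significant and starting in the TEAE window is counted by arm in SAP 7.2. PR, a conduction measure, has descriptive statistics by group. All ECG data and all AEs are listed, so what is lost from the listings is only the targeted AE display.

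Three further cautions stand:
- The protocol does not define ECG abnormalities. In the sentence on the listing, "all" qualifies the AEs, so the text does not promise a table of every abnormality of any kind or of new ones only.
- Safety analyses are descriptive, so no formal comparison of arms is lost.
- SAP 2 puts the detail of the outputs in a separate TFL shell document. Neither that document nor the SAP's index of tables (Section 15) was in the text available, so a table of the overall ECG result may exist there.

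These points limit the consequence but do not remove the gap. The AE route depends on the Investigator's judgement and on the 7-day window, and group statistics for PR do not show how many patients became abnormal. A table in the shells would answer the first omission, but not the narrower listing trigger written in SAP 7.5 or the silence of Section 11.

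**Conclusion.** The point holds as an undeclared reporting gap between protocol and SAP. It does not threaten the primary endpoint. In the SAP text, a by-arm count is lost for rhythm, ischemic and non-PR conduction abnormalities that are not reported as TEAEs. These are findings not judged clinically significant, or nonserious findings first seen at a Follow-up ECG more than 7 days after the last dose. They appear only in listings.

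The number of patients affected is not in the documents and could be zero. The conclusion assumes that the TFL shells contain no such table. The Follow-up part also assumes that the ECG rows of the Schedules of Events have been read correctly. The change is worth making because the table was planned and its source field is already collected.

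**What to change.** In SAP 7.5, unless the TFL shells already provide it:
1. Add a table, by arm, of n (%) for the overall ECG result at each scheduled ECG, including Follow-up, with a shift from the Day 1 predose baseline. Including Follow-up is consistent with the protocol's shift to end of study, since the schedule labels that visit as end of study. State which eCRF result categories count as an abnormality.
2. Extend the AE listing to participants with any post-baseline ECG abnormality, and keep the QTcF and HR triggers.
3. If repeat ECGs are to be used in the table, say so as an exception to SAP 5.1, which keeps unscheduled and repeat assessments out of summary tables. SAP 7.4 already includes unscheduled assessments for its orthostatic criteria.

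If the sponsor prefers the present outputs, Section 11 should declare the dropped table and the narrower listing and give the reason. The cost is one table and one wider listing from data already collected.

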## 7.6. Physical Examination and Weight

The physical examination data will be listed.

For weight, the number and percentage of participants with changes from baseline (defined as Table 10) of clinical interest will be summarized by treatment group for the Safety Population.

Table 10. Changes of Clinical Interest Criteria for Body Weight

Parameter	Flag	Change from Baseline
Weight, kg	High	Increase of $\geq$ 10%
	Low	Decrease of $\geq$ 10%

This document is confidential.

## 8. Pharmacodynamic (PD) Analyses

All PD analyses except the PRO analyses will be based on the Safety and Evaluable Populations. PRO analyses will be based on the ITT and Evaluable Populations. Listings will be provided for all PD-related data.

For the treatment comparisons by statistical modeling:

- comparisons between 18 mg olinciguat group vs. the matched placebo group (PBO2) enrolled under Protocol Amendments 4 and later
- comparisons between each olinciguat group (2 mg, 4 mg, 6 mg, and 18 mg) vs. the overall placebo group combined from all protocols

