### 3.2. Brief Description

This Phase 2, multicenter, randomized, double-blind, placebo-controlled, parallel-group study with a 2-week single-blind Run-in Period will evaluate the safety and pharmacodynamics (PD) of oral olinciguat compared with placebo when administered QD for approximately 12 weeks in participants with SCD.

At the Screening Visit, participants will undergo preliminary procedures to determine their initial eligibility. At the Run-in Visit (which will occur at least 3 calendar days after the Screening Visit), eligible participants will then begin 14 to 17 days of single-blind placebo dosing and will begin recording their daily and weekly symptom assessments in an electronic diary (eDiary).

On Day 1 of the Treatment Period, participants who continue to be eligible will be randomized to double-blind study drug (QD olinciguat or placebo). Note that participants enrolled under protocol Amendment 3 or earlier were randomized differently than those randomized under Amendment 4 and later, as described below.

- Under Amendment 3 or earlier: Participants were randomly assigned in a 1:1:1:1 ratio to placebo, 2 mg olinciguat, 4 mg olinciguat, or 6 mg olinciguat (see [Table 3](#))
- Under Amendment 4 and later: Participants were randomly assigned in a 3:1 ratio to 18 mg olinciguat or placebo (see [Table 4](#))

On Day 1 and for each up-titration visit, participants must remain in the clinic at least 6 hours postdose and will be allowed to leave thereafter at the Investigator's discretion.

At all scheduled study visits, participants will undergo safety, efficacy, and PK assessments and, as applicable, will take the relevant study drug dose and will be issued study drug supply for subsequent at-home QD dosing. In addition, participants will receive scheduled phone calls in between the scheduled visits to monitor TEAEs and concomitant medications and procedures. Throughout the Treatment Period, participants will continue completing the patient-reported outcome (PRO) questionnaires each day in their eDiary.

Beginning in March 2020, remote visits via phone call have been allowed to accommodate the impact of COVID-19 on study visits and participants' safety. The phone visits, when necessary, have been utilized to collect adverse event, concomitant medication, select vital sign timepoints, uptritration eligibility, and other relevant data.

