### 3.5. Treatment Assignment

During the Run-in Period, all participants will receive placebo in a single-blind manner (Table 2).

Table 2. Dose Regimen During Single-blind Run-in Period

Dosage	Run-in (Day -17 or -14 to Day -1); QD Dose
placebo daily	1×matching placebo tablet
QD=once daily	

The Treatment Period is double blind and placebo controlled. Participants will be randomized through central randomization based on the protocol applicable at the time. The computer-generated randomization schedule will be prepared by an independent statistician not otherwise associated with the conduct of the study.

Under Protocol Amendment 3 or earlier, eligible participants will be stratified by hydroxyurea (HU) use and randomly assigned in a 1:1:1:1 ratio to 6 mg olinciguat, 4 mg olinciguat, 2 mg olinciguat, or placebo at Randomization Visit on Day 1 (Table 3).

Table 3. Dose Regimen by Treatment Period Week for Participants Randomized Under Amendment 3 and Earlier

Randomized Dose Level	Week 1=half dose		Weeks 2 to 12=full dose *	
	Dosage	QD Dose	Dosage	QD Dose
6 mg IW-1701	3 mg IW-1701 daily	1 × 3-mg IW-1701 tablet	6 mg IW-1701 daily	2 × 3-mg IW-1701 tablet
4 mg IW-1701	2 mg IW-1701 daily	1 × 2-mg IW-1701 tablet	4 mg IW-1701 daily	2 × 2-mg IW-1701 tablet
2 mg IW-1701	1 mg IW-1701 daily	1 × 1-mg IW-1701 tablet	2 mg IW-1701 daily	2 × 1-mg IW-1701 tablet
Placebo	Placebo daily	1 × matching placebo tablet	placebo daily	2 × matching placebo tablet

Under Amendment 4 and later, eligible participants will be stratified by HU use and randomly assigned in a 3:1 ratio to 18 mg olinciguat or placebo (Table 4).

Table 4. Dose Regimen by Treatment Period Week for Participants Randomized Under Amendment 4 and Later

Initial Dose Level (Day 1-Day 7)		Week 1 through Week 3 (Day 8-Day 28)		Week 4 through Week 12 (Day 29-Day 85)	
QD Dose	QD Dosage	QD Dose	QD Dosage	QD Dose	QD Dosage
6 mg IW-1701 daily	2×3-mg IW-1701 tablet	12 mg IW-1701 daily	4×3-mg IW-1701 tablet	18 mg IW-1701 daily	6×3-mg IW-1701 tablet
PBO daily	2×matching PBO tablet	PBO daily	4×matching PBO tablet	PBO daily	6×matching PBO tablet

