## 5. General Aspects for Statistical Analysis

### 5.1. General Methods

All applicable data will be summarized by randomized treatment arm, unless specified otherwise. For summary tables, unless otherwise noted, participants who were randomized to placebo will be summarized as:

- 1) PBO1: participants who were randomized to placebo under Protocol Amendment 3 or earlier,
- 2) PBO2: participants who were randomized to placebo under Protocol Amendment 4 or later, and
- 3) Overall: participants who were randomized to placebo under any version of the protocol.

The participants who were randomized to olinciguat dosing regimens will be summarized as:

- 1) 2 mg: participants who were randomized to 2 mg olinciguat dosing regimen under Protocol Amendment 3 or earlier,
- 2) 4 mg: participants who were randomized to 4 mg olinciguat dosing regimen under Protocol Amendment 3 or earlier,
- 3) 6 mg: participants who were randomized to 6 mg olinciguat dosing regimen under Protocol Amendment 3 or earlier, and
- 4) 18 mg: participants who were randomized to 18 mg olinciguat dosing regimen under Protocol Amendment 4 or later

For safety analysis, the data will be summarized by treatment arm actually received.

In addition, data will be summarized by scheduled visit and/or time-point where appropriate. Unscheduled or repeat assessments will not be included in summary tables, but will be included in listings.

Continuous variables will be summarized using descriptive statistics, including the number of observations (n), mean, standard deviation (SD), median, minimum, maximum and interquartile range (IQR). Categorical variables will be summarized using frequencies and percentages. Unless otherwise specified, percentages will be based on the total number of non-missing values.

Unless otherwise specified, all confidence intervals (CIs) will be 2-sided with a confidence level of 95%. No adjustments will be made for multiplicity.

All statistical analyses will be performed using SAS Version 9.4 or later for Windows.

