### 8.1. Hemodynamics

The hemodynamic parameters are listed here:

- Change from Day 1 baseline in seated systolic and diastolic blood pressures (BPs) and pulse to predose at Weeks 1, 4, 8, and 12
- Change from Day 1 baseline in orthostatic systolic and diastolic BPs and pulse to predose at Weeks 1, 4, 8 and 12
- For each study visit (Day 1, Weeks 1, 4, 8, 12), change from predose to each postdose time point of the same visit for seated systolic BP, diastolic BP and pulse.

Details about BPs and pulse assessment are included in [Section 7.4](#). An orthostatic measurement is derived by subtracting the seated measurement from the standing measurement.

Descriptive statistics will be tabulated for each hemodynamic parameter by treatment group. In addition, an analysis of covariance (ANCOVA) model will be fitted with change from baseline as dependent variable, treatment group, and stratification factor (HU use) as fixed effects, and corresponding baseline value as covariate, at each visit/time point. Pairwise contrasts will be used to compare each olinciguat group with the placebo group. Least-squares means (LSMs) for each treatment group, LSM differences between each olinciguat group and the placebo group, their corresponding 2-sided 95% CIs, and p-values will be presented. Example SAS code for ANCOVA model is shown below:

```
Proc mixed data = analysis_data;
  class stratum trt;
  model chg = base stratum trt;
  lsmeans trt/ cl diff;
run;
```

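### SAP Section 8 lists a concurrent-placebo contrast for 18 mg, but only a placebo group pooled over two randomisations for 2, 4 and 6 mg

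*SAP*

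**What the plan says.** The SAP describes two randomisations. Section 3.2 notes that "participants enrolled under protocol Amendment 3 or earlier were randomized differently than those randomized under Amendment 4 and later". Under Amendment 3 or earlier (Section 3.5), participants were "randomly assigned in a 1:1:1:1 ratio to 6 mg olinciguat, 4 mg olinciguat, 2 mg olinciguat, or placebo". For the second cohort the same section says: "eligible participants will be stratified by HU use and randomly assigned in a 3:1 ratio to 18 mg olinciguat or placebo".

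Section 5.1 defines three placebo groups for summary tables. The first is "PBO1: participants who were randomized to placebo under Protocol Amendment 3 or earlier"; the others are PBO2 (Amendment 4 or later) and the two combined.

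For modelled comparisons, Section 8 lists two items:
- The first concerns the highest dose alone: "comparisons between 18 mg olinciguat group vs. the matched placebo group (PBO2) enrolled under Protocol Amendments 4 and later"
- The second takes in all four doses: "comparisons between each olinciguat group (2 mg, 4 mg, 6 mg, and 18 mg) vs. the overall placebo group combined from all protocols"

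There is no third item setting 2, 4 or 6 mg against PBO1.

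The individual analyses name the comparator in different ways:
- **ANCOVA (8.1):** "Pairwise contrasts will be used to compare each olinciguat group with the placebo group". The example code models baseline, HU stratum and treatment, and takes differences with "lsmeans trt/ cl diff".
- **MMRM (8.3.2):** adds visit and treatment-by-visit, but no cohort term. Section 8.4.1.2 reuses it against a placebo group described only as specified.
- **Log-rank and CMH (8.2.1, 8.3.1, 8.4.1.1):** refer to the corresponding placebo group without defining it by dose. The CMH test controls for HU use only.
- **Wilcoxon test of the annualised VOC rate (8.2.1):** names no comparator.

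**The concern.** Randomisation protects a comparison only within the cohort that was randomised together. The 2, 4 and 6 mg patients were randomised against PBO1. The PBO2 patients entered later, under a different allocation ratio and treatment schedule. In the pooled contrast, any difference between the cohorts in baseline-adjusted change is therefore attributed partly to the dose. The plan gives 18 mg a contrast free of this problem and gives the low doses none in its list of modelled comparisons.

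The cohorts differ in at least one documented respect. Placebo patients took 1 then 2 tablets a day in the first cohort, and 2, 4 then 6 in the second (SAP Section 3.5, Tables 3 and 4). Whether that changes any outcome is unknown.

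At stake are the low-dose estimates, confidence intervals and p-values for the exploratory PD and PRO endpoints. A dose-response reading across 2, 4, 6 and 18 mg would draw on them.

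**Working it through.** **Inputs.** About 40 patients in the first cohort and about 48 in the second (SAP 3.4); allocation 1:1:1:1 and 3:1 (SAP 3.5); two-sided 95% intervals (SAP 5.1). The stated total reproduces: 40 + 48 = 88. It is not a power-based figure, and the documents give no SD, effect size or drift. Results below are therefore in SD units, and the drift d is an assumption shown over a range.

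**Arm sizes.**
- First cohort: 40/4 = 10 each on 2, 4, 6 mg and PBO1.
- Second cohort: 48 × 3/4 = 36 on 18 mg; 48 × 1/4 = 12 on PBO2.
- Pooled placebo: 10 + 12 = 22.

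**Non-concurrent share.** For 2, 4 and 6 mg it is 12/22 = 54.5%. For 18 mg it is 10/22 = 45.5%, but 18 mg also has its PBO2 contrast.

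**Bias.** If the cohorts differ by d in adjusted change, the pooled low-dose contrast is off by (12/22) × d = 0.545d. The sign can go either way.

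**Standard errors**, from √(1/n₁ + 1/n₂):
- Low dose vs pooled placebo: √(1/10 + 1/22) = 0.381
- Low dose vs PBO1: √(1/10 + 1/10) = 0.447
- Ratio: 0.447/0.381 = 1.17

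**Type I error, low dose vs pooled placebo.** With z = bias/0.381, the normal approximation is Φ(−1.96 − z) + 1 − Φ(1.96 − z). The next column uses a noncentral t with 81 df. The last comes from 40,000 simulated trials of 88 per drift value, analysed by ANCOVA with HU and baseline.

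| Assumed d (SD) | Bias (SD) | z | Normal | Noncentral t | Simulation |
|---|---|---|---|---|---|
| 0 | 0 | 0 | 5.0% | 5.0% | 4.9% |
| 0.25 | 0.136 | 0.358 | 6.5% | 6.4% | 6.6% |
| 0.5 | 0.273 | 0.715 | 11.0% | 10.9% | 10.5% |
| 1 | 0.545 | 1.430 | 29.8% | 29.3% | 26.9% |

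The simulated figure at 1 SD is lower because drift inside the pooled placebo group also inflates the residual variance. In the same simulations, with PBO1 and PBO2 as separate levels, 2 mg vs PBO1 stayed between 4.9% and 5.2% at every drift.

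**Break-even.** Pooling has the smaller mean squared error while 0.381² + (0.545d)² < 0.447². That gives d < √(0.447² − 0.381²)/(12/22) = 0.428 SD.

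**Can the data show which side applies?** PBO1 minus PBO2 has SE √(1/10 + 1/12) = 0.428. With t = 1.990 (80 df), its 95% half-width is 0.852 SD. Power to detect a 0.5 SD drift is about 21%.

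**Precision given up.** At a true effect of 1 SD, power is about 60% for 10 vs 10, against 74% for 10 vs 22 with no drift.

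**The case against.** The strongest reply is that pooling is openly stated and reasonable. Section 8 says plainly what is pooled. Section 5.1 shows PBO1, PBO2 and overall placebo in separate columns, so a reader can set the low doses beside PBO1. The analyses are exploratory and unadjusted for multiplicity, and with 10 patients per low-dose arm a preference for precision is defensible. Every inflated error rate above depends on an assumed drift. All of this stands. It supports keeping the pooled contrasts. It does not explain why 18 mg receives a concurrent contrast and the low doses do not, and descriptive columns supply no adjusted difference, interval or p-value.

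A second reply is that the wording of the CMH and log-rank tests may already mean PBO1 for the low doses. That is a natural reading of a corresponding placebo group, and Protocol Section 5.1.2 uses a similar phrase. The other reading, back to the Section 8 list, gives overall placebo. For these tests the point is therefore an ambiguity and not a clear omission. The omission is firm for the ANCOVA and MMRM.

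A third reply is that table-level detail sits in the TFL shells, which are not available here. They may settle the comparators. The SAP should still name them, because it governs the analysis.

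A reader might also infer that pooling is an undeclared departure from the protocol, since SAP Section 11 does not mention it. The documents do not support that: Protocol Section 5.1.1 speaks of the placebo arm in the singular, which does not exclude one combined group.

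**Conclusion.** The point holds as a minor gap in the list of modelled comparisons. Section 8 plans a concurrent contrast for 18 mg and none for 2, 4 or 6 mg, while 12 of 22 pooled controls are non-concurrent for those doses and neither the ANCOVA nor the MMRM adjusts for cohort. The bias is 0.55 times whatever cohort difference exists. The size rests on planned arm sizes, a common within-cohort SD and an assumed drift.

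It is tempting to read this as showing that the low-dose results are biased or that their error rate is inflated. The documents do not show that. They contain no evidence on drift, and below about 0.43 SD the pooled estimate is the better one by mean squared error. Nor does the point reach the primary safety objective, which is descriptive, or remove the 18 mg concurrent contrast, which is already planned.

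**What to change.** In SAP Section 8, add a third item to the list: each of 2 mg, 4 mg and 6 mg olinciguat compared with PBO1, the placebo patients randomised alongside them under Amendment 3 or earlier. Keep the overall-placebo comparisons as a second set.

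Then state how each set is obtained:
- **ANCOVA and MMRM:** concurrent contrasts from a fit with PBO1 and PBO2 as separate treatment levels; pooled contrasts from a fit with a single placebo level. The PBO1 minus PBO2 difference with its interval may be shown for these models, but is optional because it is unlikely to be informative.
- **CMH, log-rank and Wilcoxon tests:** the corresponding placebo group is PBO1 for 2, 4 and 6 mg and PBO2 for 18 mg, with the test against overall placebo reported as the second comparison.

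The cost is SAP wording and programming; no new data are needed. One treatment coding in the example code cannot give both sets of differences, so two fits per endpoint are required. Listed contrasts per endpoint and visit rise from 5 (18 mg vs PBO2, plus four doses vs overall) to 8, all exploratory and unadjusted. The low-dose concurrent contrasts carry the wider standard error shown above, which is why the pooled set is kept beside them.
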